The incidence of lymphoedema following cancer treatment is a concern worldwide, affecting quality of life and limb function. There are limited studies available on the benefits vibrational therapy for lymphoedema with scientific rigour. This trial will provide an opportunity for a comprehensive investigation into vibrational therapy and how the vibration influences body tissues and functions on people affected with leg lymphoedema following cancer treatment. This trial includes a control design, with participants measured at the same timings as in the treatment group but conducting their normal lymphoedema care. Participants would be randomly selected into the control group or treatment group and then a cross over design employed. This research will aid in providing data on the effects of vibrational therapy for the maintenance of leg health in those with lymphoedema.

Hypothesis and/or Research Question

That daily 30 minutes of CVT externally applied to a lymphoedematous leg over 3 weeks has an impact on blood flow into and out of the treated limb, influencing limb extracellular fluids and volume.

Aims -

To determine the impact of 30 minutes of daily CVT over 3 weeks on blood flow, fluid content and limb size of legs of participants affected with lymphoedema following cancer treatment.

To determine the efficacy of home delivered CVT on leg lymphoedema following cancer treatment through use of a TGA-approved massage pad.

Objectives -

To better understand the impact of CVT on blood flow into and out of the major vessels of lymphoedematous legs, compared to a normal lymphoedema care

To measure main arterial inflow and venous outflow from the treated and non-treated legs using

ultrasound sonography.

To measure total leg fluid volume changes using Bioimpedance Spectroscopy and Perometry.

To measure skin integrity changes using indurimetry.

To measure skin moisture changes of the lower leg using a portable moisture meter.

Expected outcomes -

Change in arterial inflow, venous outflow in the main vessels of the lower limb and a concomitant change in limb size and volume.

Project design

Anticipated start and finish dates: May 2024 (as soon as ethics approval is received) to Nov 2025

Estimated last first participant enrolled: May 2024

Estimated date last participant completed: September 2025

Study Sites/Settings:

- Lymphoedema Clinical Research Unit, Flinders University

Recruitment target:

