Estimated sample size of 30 final participants based on our current best knowledge based on prior trials of the pad we have conducted.

Methodology - clearly describe the specific procedures or techniques that will be used to answer the research question and meet the aims.

Participants will be randomly allocated into either the treatment or control group by odd vs even number selection. In the control group, participants will conduct their normal lymphoedema care routine. In the treatment group, the participant's lymphoedematous leg will be treated with the Niagara® Cyclopad for a total of 30 minutes (i.e. 10 minutes each in three locations; lower back, upper leg and lower leg) using the set minimum frequency. There will be 5 cycles of deep breathing before and after the massage pad use. Participants will be asked to rest supine for 15 mins prior to starting each treatment. At the end of their 4-week follow-up period, the participant will be crossed over into the other group.

Measurement points are:

- Screen
- Baseline
- Day 1/2 (phone call)
- Day 4
- 1 week
- 2 weeks
- 3 weeks
- 2 weeks Follow-up
- 4 weeks Follow-up

Please see Table 1 for Schedule of assessments.

Procedure	SCREEN	BASELINE	PHONE CALL (Day 1 or 2)	DAY 4	WEEK 1	WEEK 2	WEEK 3	FOLLOW-UP 1 (2 weeks)	FOLLOW-UP 2 (4 weeks)	
			Treatment or Control Phase						Post-Treatment/Control Phase	
Visit	1	2	3	4	5	6	7	8	9	
Informed Consent	✓									
Eligibility Criteria	✓									
Demographics	✓									
Medical History	✓									
Physical Exam	✓	✓								
Vital Signs	✓	✓		✓	✓	✓	✓	✓	✓	
Height	✓	✓								
Weight	✓	✓		✓	✓	✓	✓	✓	✓	
LYMQOL		✓					✓	✓	✓	
Symptom Scale (10-point Likert)		✓					✓	✓	✓	
Bioimpedance	✓	✓		✓	✓	✓	✓	✓	✓	
Limb Volume	✓	✓		✓	✓	✓	✓	✓	✓	
MoistureMeter D		✓		✓	✓	✓	✓	✓	✓	
Tonometry/Skin FibroMeter		✓		✓	✓	✓	✓	✓	✓	
Concomitant Medications	✓	✓		✓	✓	✓	✓	✓	✓	
Review Participant use of device in-situ			✓							
Review Participant Diary			✓	✓	✓	✓	✓			
Sonography		✓					✓	✓		

crossover to other group

Procedure	BASELINE	PHONE CALL (Day 1 or 2)	DAY 4	WEEK 1	WEEK 2	WEEK 3	FOLLOW-UP 1 (2 weeks)	FOLLOW-UP 2 (4 weeks)	
			Treatment or Control Phase					Post-Treatment/Control Phase	
Visit	10	11	12	13	14	15	16	17	
Informed Consent									
Eligibility Criteria									
Demographics									
Medical History									
Physical Exam	✓								
Vital Signs	✓		✓	✓	✓	✓	✓	✓	
Height	✓								
Weight	✓		✓	✓	✓	✓	✓	✓	
LYMQOL	✓					✓	✓	✓	
Symptom Scale (10-point Likert)	✓					✓	✓	✓	
Bioimpedance	✓		✓	✓	✓	✓	✓	✓	

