- Principal Investigator– [name]
- Study Coordinator – [name]

How much time will participants have to consider participation?

Potential participants will be given at least one week to consider participation in the study but can take more time if required.

Will there be an opportunity to confirm or renegotiate consent during the research project:

- Yes
 No

Who will be confirming or renegotiating consent with participants?

Principal Investigator or Study Coordinator

What process will be undertaken and how will participants be supported through this process?

Staff will be available at all times at appointments and via phone call to discuss any participant changes to consent.

Waiver of consent/Pre-screen Waiver of consent

Are you requesting a waiver of consent to pre-screen a data source for the purpose of identifying eligible potential candidates to invite to participate in this study? No

Are you requesting a waiver of consent and no participant information sheet or consent form will be used for this study?

- No
 Yes - **The waiver of consent must be justified using the National Statement chapter 2.3.9 and 2.3.10**

(a) to (i).

Please:

- (a) Demonstrate how involvement in this research carries no more than low risk to participants. Refer to The National Statement chapters 2.1.6 and 2.17 for guidance.**

- (b) Explain how the benefits from the research justify any risks of harm associated with not seeking consent**

- (c) Explain why it is impracticable to obtain consent (for example, due to the quantity, age or accessibility of records).**

- (d) Explain why there is no known or likely reason for thinking that participants would not have consented if they had been asked.**

- (e) Demonstrate there is sufficient protection of their privacy.**

- (f) Demonstrate there is an adequate plan to protect the confidentiality of data.**

- (g) Explain in the case the results have significance for the participant's welfare there is, where practicable, a plan for making information arising from the research available to them i.e. via a disease-specific website or regional news media).**

- h) Explain the possibility of commercial exploitation of derivatives of the data or tissue will not deprive the participants any financial benefits to which they would have been entitled.**

- (i) Demonstrate the waiver is not prohibited by State, Federal or international law.**

Participant selection and activities

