How are potential participants identified as suitable for the research?

Advertisement notice attached separately. Participants will be recruited from the local lymphoedema clinics and by word of mouth from those who decided to participate. Advertisement will be placed on relevant notice boards in clinics. All will be provided with the full details (see PICF) if they express verbal interest.

How will participants be recruited into the study?

Potential participants will see advertisement and then on the basis of that decide if they wish to participate. We anticipate some interest by word of mouth and in these cases the potential participant will be provided with the advertisement, followed by the PICF if still interested.

Who is approaching the participants about this research project?

Self-identification through awareness of the ad or Lymphoedema Therapist will notify a potential participant of the study.

When is this occurring?

Clinic – a lymphoedema therapist will notify the potential participant that the trial is available.

Are participants reimbursed for parking, travel or time involved?

- No
 Yes

Please detail what is being reimbursed and the amount:

Participants will be reimbursed \$10 for parking and provided a \$10 gift voucher for a light meal or drink at a local café. Participants will be able to keep the massage pad provided to them during the trial at the end of the study.

Participant commitment -

Participants will have 17 appointments over the full crossover study design (from screening to 4 week follow-up). Two of these visits will be a phone call (Day 1 or 2). Assessments are non-invasive and outlines in the Methodology Section.

Participant follow up –

Participants have clinic appointments at Screening, Week 1, Week 2, Week 3, 2-week Follow-Up and 4-week Follow-Up (for both the treatment and control arm). There will be a phone call on Day 1 or Day 2 to monitor progress and home use of the massage pad.

Ethical considerations

Please describe the risk and burden associated with your research.

This research is of no risk of harm or discomfort and no risk for minor burden or inconvenience. The only foreseeable risk is no greater than discomfort. The massage pad is a TGA-approved medical device, class IIa (ARTG 151788) and the assessments are non-invasive. There is a risk the quality of life questionnaire (LYMQL) may cause distress. Counselling will be provided if required.

How will any risks be managed?

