Participant is free to withdraw from the study if they find the treatment discomforting.

Benefits – please identify and explain the expected outcomes and benefits of the study

The outcome will be an improved understanding of the impact of CVT on the blood flow into and out of lymphoedematous legs and of its impact on overall leg and fluid volumes. As well as perceived impact of the participant on symptoms and quality of life and use of the device.

Does a dependant or unequal relationship exist between the participant and the researcher?

- Yes -
How will the dependant / unequal relationship be managed?
 No

Conflicts of interest: Please refer to the National Statement chapter 5.4, and your institutional policy for guidance.

- Yes / No

Please provide details of the conflict of interest and how it will be managed:

Data management plan

Which listed investigators will collect the study data / information?

SC will collect all data and enter into an Excel spreadsheet (located on Flinders University password-protected computer drive). Sonographer will collect ultrasound data and SC will enter this into the spreadsheet.

What type of data will be used?

- Data that has never been labelled with individual identifiers or from which identifiers have been permanently removed, and by means of which no specific individual can be identified.
- Identifiable - data that contains an identifier or combination of identifiers i.e. name, date of birth, image, address, URN
- Data in which identifiers have been removed and replaced by a code, but it remains possible to re-identify a specific individual by, for example, using the code or linking different data sets.

If the data being used has the potential to identify a patient, please justify and describe how accidental re-identification will be avoided?

Any identifying codes will be removed and replaced by numbers only.

If the participant's medical records are being accessed - please state where the information is being collected

N/A

Data sets -

Ultrasound doppler – flow rates, flow volumes from major artery and veins on both legs, as per the data output from the Doppler unit. This is then transcribed into an excel data sheet.

Perometry - the total volume and circumferences of both limbs are noted from the perometry program and transcribed into the excel data sheet.

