Matching and sampling strategies: Participants will be randomly allocated into either the treatment or control group by odd vs even number selection. After the 4 week follow-up period, the participants will be crossed over into the other group (treatment or control). In the event a participant does not wish to participate in the second group then either another participant who intends to participate in both will be chosen or a second participant chosen with matching bio data (Age, gender, BMI).
Accounting for potential bias, confounding factors and missing information: Randomisation will help avoid bias. We will also be able to observe if there are conditions such as psoriasis, infection etc on the limbs and exclude participants if not declared in initial responses. Missing information is unlikely due to the short time of the intervention and measurement period. Should it occur due to equipment failure then the participant could be invited to return. Failing this the data set would be excluded from the analysis
Sample size and statistical or power issues –

This study is one following information collected from a prior pilot trial and has informed us a sample size of 30 is adequate. While a statistical outcome is useful, we also will examine what we see as “biological” or “practical” changes. However, given the relative homogeneity of the sample and the fact that we do not intend to undertake or rely on any subgroup analysis the sample size of 30 is adequate. The equipment we use i.e., perometry is able to accurately and detect changes in limb volumes of 50ml in a 5000ml limb section and our Bio-impedance analysis unit can detect fluid changes of 10ml per limb.

How will you measure, manipulate and/or analyse the information collected?

All data will be used in its raw form as generated by the measuring equipment. Analysis initially by excel and followed by analysis using STATA or similar statistical program as appropriate.

Data linkage – what linkages are planned or anticipated?

None

Participants may withdraw from the study by choice, what impact will a participant withdrawing have on the data?

Should they withdraw, they will be replaced by another matched participant completely or for the arm of the trial that they withdrew from. Given the massage pad is available on the market and this is low risk research, we don't anticipate many participants to withdraw.

How will this be responded to?

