Once the participant has let the research team know that they wish to withdraw, the withdrawal will be documented. If the participant wishes a follow-up on lymphoedema status, this will be conducted. A participant may provide the research team with the reason(s) for leaving the study, but is not required to provide their reason.

Results, reporting, outcomes, and future plans

Please detail your plans for the return of the research results to the participants:

Participants will be given a copy of the data gained from the Perometer, the BIS analyser (giving them details of their BMI, muscle, fats, fluids and a fitness score similar to those given at gyms) at the end of each clinic appointment. They will also be given a copy of the overall study results.

What are your plans for dissemination and publication of project outcomes?

We would intend to present research outcomes at the Australasian Lymphology Association meeting in 2025 as it has relevance to disorders such as lymphoedema and chronic oedema.

Will you be providing a de-identified data set to the journal for verification purposes?

All data collected is de-identified and will have a re-identification code so that the remaining information does not identify an individual.

Please detail other potential uses of the data at the end of the project:

Inform us of what benefits might come from massage pad use in lymphoedema at the base frequency setting.

What are your plans for sharing and/or future use of data and/or follow-up research? i.e., anticipated secondary use of data:

If results are publishable and presentable, we plan to share with publications and conferences; including conferences with community engagement. De-identified results will be shared with Sponsor. The results will inform us on the direction of any future research in this area, including if vibration therapy, an easily applied, non-invasive therapy, can optimise outcomes for lymphoedema management. If a benefit is measured, infrared and indocyanine green imaging studies would be considered to detail the response of the lymphatics through location and function before and after treatment, as well as research of the effect of this therapy on other lymphatic conditions.

What is the project closure process?

Final HREC report and report to the sponsor. Destruction of the data after 5 years.

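### Replacing people who withdraw with matched substitutes puts non-randomised people in vacant arms, loses the within-person comparison for one-arm places, and can favour completers

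*Protocol*

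**What the plan says.** The trial is a randomised crossover of home pad use against normal lymphoedema care. The Recruitment target gives "Estimated sample size of 30 final participants". Two rules in the Analysis section govern people who do not complete:

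- The answer on what a withdrawal does to the data: "Should they withdraw, they will be replaced by another matched participant completely or for the arm of the trial that they withdrew from".
- Matching and sampling strategies, for someone unwilling to enter the second group: "either another participant who intends to participate in both will be chosen or a second participant chosen with matching bio data (Age, gender, BMI".

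Other relevant text:

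- After a withdrawal (How will this be responded to?): "If the participant wishes a follow-up on lymphoedema status, this will be conducted". Giving a reason is optional.
- Ethical considerations, on risk: "The only foreseeable risk is no greater than discomfort". The same answer adds possible distress from the quality-of-life questionnaire, and also says that there is no risk of discomfort, so it is not consistent with itself.
- How will any risks be managed?: "Participant is free to withdraw from the study if they find the treatment discomforting".
- Consent: "Staff will be available at all times at appointments and via phone call to discuss any participant changes to consent".

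The protocol expects few withdrawals but gives no rate.

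**The concern.** A crossover gains its strength from comparing each person with himself or herself, in an order set by chance. A one-arm substitute supplies neither. The vacancy, not randomisation, decides which condition the substitute receives, and the pad-minus-control contrast for that place is a difference between two people. A substitute for a second-period place also has no first period behind them.

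Complete replacement avoids the mixing, but builds the set of 30 from people who finish. Pad discomfort can arise only in the pad period, since the control period is usual care. Age, gender and BMI do not measure tolerance of the pad. If some people leave because of the pad and finishers take their places, the pad-period data represent those who tolerate it.

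The hypothesis is that the therapy "has an impact on blood flow into and out of the treated limb, influencing limb extracellular fluids and volume". Blood flow is the most exposed part, because Table 1 schedules no scan between baseline and Week 3. Placing a substitute and not holding a visit are matters of conduct. A later analysis plan can decide which data to use, but it cannot randomise a substitute already placed or recover a visit that never took place.

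**Working it through.** **Plan's own figure.** The 30 cannot be reproduced: no significance level, power, effect size, standard deviation or dropout rate is given. It is used below only as the number of completed places.

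**Step 1. What each rule does to one place.**

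| Event | Replacement | Both periods from one person? | Substitute's arm |
|---|---|---|---|
| Withdraws | Complete | Yes | Allocation not described |
| Withdraws | One arm | No | Set by the vacancy |
| Declines second group | New person doing both | Yes | Allocation not described |
| Declines second group | Matched person (read as filling that group only) | No | Set by the vacancy |

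**Step 2. Post-baseline measurements lost in a period (Table 1).** Volume, bioimpedance, moisture and induration: Day 4, Weeks 1, 2 and 3, Follow-ups 1 and 2, so 6. Sonography: Week 3 and Follow-up 1, so 2. LYMQOL and symptom scale: Week 3 and Follow-ups 1 and 2, so 3.

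| Leaves after | Lost of 6 | Scans lost of 2 | Questionnaire scores lost of 3 |
|---|---|---|---|
| Day 4 | 5 | 2 | 3 |
| Week 1 | 4 | 2 | 3 |
| Week 2 | 3 | 2 | 3 |
| Week 3 | 2 | 1 | 2 |

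Someone who leaves the pad period before Week 3 therefore gives no pad-period change in blood flow, LYMQOL or symptoms. The Quantitative Data text lists sonography at every clinic presentation. If that governed instead of Table 1, some early leavers would have a scan.

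**Step 3. Share of pad starters without a blood-flow change (assumed k).** If k people leave the pad period before Week 3 and are replaced until 30 finish, the share is k/(30+k): 0% for k = 0, 1/31 = 3.2%, 2/32 = 6.3%, 3/33 = 9.1%. This is a share missing, not a bias.

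**Step 4. What that share could do (assumed e).** Let the pad effect be 1 in those who stay and e in those who leave. The mean over all starters is (30 + ke)/(30 + k), and an analysis of the 30 finishers overstates it by (30 + k)/(30 + ke) − 1.

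- e = 0: k/30, which is 3.3%, 6.7% and 10.0% for k = 1, 2, 3.
- e = 0.5: 0.5/30.5 = 1.6%, 1/31 = 3.2%, 1.5/31.5 = 4.8%.
- e = 1 (leaving unrelated to the effect): 0%.

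**Step 5. Cost of mixed pairs (assumed k and r).** Let r be the correlation between one person's two periods, and take the substitute as uncorrelated with the person replaced. If k of 30 pairs are mixed, the variance ratio of the mean pad-minus-control difference is

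[(30 − k)(1 − r) + k] / [30(1 − r)] = 1 + (k/30) × r/(1 − r).

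- r = 0: 1.00.
- r = 0.5: 1 + 1/30 = 1.03 (k = 1); 1 + 3/30 = 1.10 (k = 3).
- r = 0.8: 1 + 4/30 = 1.13 (k = 1); 1 + 12/30 = 1.40 (k = 3).

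These are upper values for each r. If matching gave a correlation of 0.2, the last factor becomes (r − 0.2)/(1 − r). At k = 3 the ratio falls to 1 + 0.1 × 0.3/0.5 = 1.06 for r = 0.5, and 1 + 0.1 × 0.6/0.2 = 1.30 for r = 0.8.

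**The case against.** The strongest reply is that the rules do limited harm. Complete replacement keeps both periods in one person. Each period has its own baseline, so even a one-arm substitute gives a within-person change for that period. Perometry, bioimpedance and Doppler cover both legs. Few withdrawals are expected, and the Day 1 or 2 call checks pad placement and may settle early discomfort. All of this stands. It confines the loss of pairing to one-arm places, where the loss is of the pad-minus-control contrast and not of all within-person information.

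The direction of any tilt is also open. A schedule of 17 appointments could cause withdrawal in either period. Someone given the pad first who declines the second group is declining control, so the substitute supplies control data. Participants keep the pad at the end, which is a reason to stay. A reader might infer that the protocol shows withdrawal to be driven by the pad; it shows only that this could happen.

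Three further inferences are tempting and not supported:

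- That data from people who withdraw are discarded. No text says so. The exclusion rule for missing information is written for equipment failure, and the choice of analysis set may be left to an analysis plan.
- That stopping the pad ends participation. The risk answer offers freedom to withdraw but does not equate the two, and consent can be discussed again.
- That trial visits after withdrawal happen only on request. The follow-up sentence concerns lymphoedema status and reads as a clinical offer.

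None of this justifies filling a randomised arm with a matched person.

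**Conclusion.** The point holds in a limited form. The protocol itself fixes a replacement rule that, in its one-arm version, puts a person in an arm without randomisation and loses the pad-minus-control pairing for that place. In its complete version the rule keeps the pairing but favours completers. A reader might go further and say that all replacement breaks the within-person comparison, or that the pad data are biased toward tolerators. The first is wrong for complete replacement. The second requires withdrawal to be related to the pad, which is plausible and not established.

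The bias is probably small and cannot be computed from the protocol. The figures in the working rest on assumed numbers of leavers (up to 3), effects in leavers, and correlations; the protocol gives none of these. The change should be made, because it is cheap and has to be in place before anyone withdraws. Confidence is medium.

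**What to change.** - **Analysis section (matching and sampling; withdrawal).** Remove matched substitution, above all for one arm. Keep the available data of everyone randomised in the treatment comparison, under their assigned sequence and period. Randomise any added recruit as a new participant to both periods.
- **How will any risks be managed?** State that stopping the pad is not withdrawal from the study.
- **How will this be responded to?** Invite those who stop the pad, unless they decline, to attend the remaining scheduled visits and the other period. This does not apply to people who withdraw consent.

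The cost is wording in these places and in the information sheet; the visits are already scheduled. Some who stop will decline to attend, so the gap will not close fully, and the estimated effect may be slightly smaller. A full new recruit may cost more than a one-arm substitute: Funding gives $11,870.55 per participant and no separate figure for one arm.

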Limb Volume	✓		✓	✓	✓	✓	✓	✓	
MoistureMeter D	✓		✓	✓	✓	✓	✓	✓	
Tonometry/Skin FibroMeter	✓		✓	✓	✓	✓	✓	✓	
Concomitant Medications	✓		✓	✓	✓	✓	✓	✓	
Review Participant use of device in-situ		✓							
Review Participant Diary		✓	✓	✓	✓	✓			
Sonography	✓					✓	✓		

Table 1 – Schedule of Assessments.

Brief general medical history questionnaire

A brief general medical history questionnaire will be taken at baseline regarding age, current and past illnesses, the nature of the intervention causing the chronic oedema/lymphoedema, number of lymph nodes removed, radio therapy, adjunct therapy, any medications, exercise status and regime and lymphoedema care routine.

Quantitative Data

Height, weight, heart rate, blood pressure will be taken and recorded at each clinic appointment.

At each presentation at the clinic during treatment and follow-up periods, the following measurements will be taken. Assessment will include the standard assessment procedures currently used in the Lymphoedema Clinical Research Unit (they all have prior ethics approval for many trials and are part of normal diagnostic tools):

- Perometry to measure total limb volume
- Bio-impedance Spectroscopy (BIS) for total fluids
- Indurometry measurement in lymphatic territories (3 sites)
- Moisture-meter measurement fluids in lymphatic territories (3 sites)
- Sonography for measurement of blood inflow and outflow and volumes and velocities

Perometry (opto-electronic) measurement to obtain both total leg volumes. This equipment is non-invasive and involves a frame being moved up and down the legs in a period of about 10 seconds. This equipment has been used in all prior trials approved by ethics committee and is in wide use here and around the world to assess total limb volumes and their changes.

Bioimpedance Spectroscopy measurement of both leg fluid volumes. The participant stands on a metal platform and holds hand grips. Time required for this measurement is 1-2 minutes. This is non-invasive and involves the generation of a range of frequencies, which travel through the tissues of the arms and legs. Different tissues/fluids and their contents lead to different impedances to electrical flow leading to an overall body composition reading. Of particular interest are the fluid levels in the extracellular compartments of the legs.

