Ultrasound doppler to measure blood flow (used in FMC and other vascular clinics), paying attention to flow volumes and velocities at the location of major femoral vein and artery in each of the lower limbs, near the groin area. This will be performed with participants lying on a bed and take between 3-7 minutes.

Moisture Meter analysis to measure the moisture content in the skin of the legs using a portable device that tests the bioelectric impedance of the skin. It passes a painless and safe electrical current through the skin measuring how long the current takes to travel from one sensor to the other. A determinant of the moisture level of the skin is made.

Indurometry to measure the skin integrity using a portable device that measures how hard the tissue is (tissue's resistance to compression). It is a painless measure of induration of the skin and upper subcutis noninvasively.

Qualitative Data

Symptom Scale (10-point Likert)

Participants will be asked to rate 10 symptoms commonly associated with limb swelling such as tightness, heaviness, cramps, skin dryness burning feelings etc using a 10 point Likert scale. (1 = no problem or issue to 10 = worst imaginable problem or issue).

Quality of Life impact

A Leg LYMQQL will be administered prior to and at the end of the treatment and follow-up periods. This is a validated instrument to measure the impact of leg lymphoedema on a patient's quality of life developed by [name].

Feedback

On Day 1/2 after treatment/placebo, a follow-up phone call will be made by the LCRU staff member to record any feedback regarding of treatment and ascertain proper placement of the pad during treatment. This will be an unstructured open-ended interview.

Participants will be asked to provide any comments about using the massage pad after the 3-week use. This will be documented and emergent themes viewed.

Consumer and Community engagement –

The Unit has a close affiliation with the local and national support and advocacy groups. The PI is patron of the national support group Lymphoedema Association Australia and regularly discusses potential studies with these groups.

What are your outcomes for the research and how are they measured?

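### Participants receive their limb-volume and fluid results after every clinic visit of an unmasked crossover, so later self-ratings and self-care can respond to interim outcome data

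*Protocol*

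**What the plan says.** Under the heading on results, reporting, outcomes and future plans, the protocol answers the question about returning results as follows: "Participants will be given a copy of the data gained from the Perometer, the BIS analyser". The same sentence lists body-composition items and ends with "a fitness score similar to those given at gyms) at the end of each clinic appointment". The overall study results are promised in addition.

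Both instruments supply outcome data. The objectives name total leg fluid volume change by BIS and perometry. The Quantitative Data section lists "Perometry to measure total limb volume" and says of BIS: "Of particular interest are the fluid levels in the extracellular compartments of the legs". On frequency it states: "At each presentation at the clinic during treatment and follow-up periods, the following measurements will be taken".

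The self-rated measures are the 10-symptom scale and the leg LYMQOL, which "will be administered prior to and at the end of the treatment and follow-up periods". The outcomes section counts the participant's perceived impact on symptoms and quality of life among the study's outcomes.

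Under Methodology, control participants follow their usual lymphoedema care. The Feedback paragraph mentions a placebo once, but no sham device is described anywhere.

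**The concern.** Participants can follow their own efficacy results while the trial runs, and they know whether each result belongs to a pad period or a control period. Two routes to bias follow.

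1. **Self-ratings.** A participant who has seen leg volume fall with the pad, or stay level without it, can score symptoms and LYMQOL accordingly at the next questionnaire. The score then partly reflects the printed measurement as well as how the leg feels.
2. **Behaviour.** Control care is the participant's own routine, and the pad is used at home. A participant who dislikes the latest reading can change self-care or pad use. That would act on limb volume and fluid themselves, and a change made in period 1 may persist into period 2.

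The Analysis section relies mainly on randomisation to guard against bias, together with excluding participants who have undeclared limb conditions. Randomisation balances participants at allocation. It does not protect against reactions that arise afterwards. No analysis can later separate these reactions from the effect of the pad.

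**Working it through.** The plan gives no figure for this point, so the check is a count of visits in Table 1 set against the handover rule.

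**Clinic visits at which results are handed over.** "Participants will have 17 appointments over the full crossover study design", and two of these are phone calls (Visits 3 and 11). That leaves 17 − 2 = 15 clinic visits: 1, 2, 4–10 and 12–17. Table 1 ticks limb volume and bioimpedance at all 15.

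**Visits with questionnaires.** Table 1 ticks LYMQOL and the symptom scale at Visits 2, 7, 8, 9, 10, 15, 16 and 17.

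**Sets of results already received before each questionnaire** (earlier clinic visits only, because that day's copy comes at the end of the visit):

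| Questionnaire | Earlier clinic visits | Sets received |
|---|---|---|
| Visit 2, baseline, period 1 | 1 | 1 |
| Visit 7, week 3, period 1 | 1, 2, 4, 5, 6 | 5 |
| Visit 8, 2-week follow-up | plus 7 | 6 |
| Visit 9, 4-week follow-up | plus 8 | 7 |
| Visit 10, baseline, period 2 | plus 9 | 8 |
| Visit 15, week 3, period 2 | plus 10, 12, 13, 14 | 12 |
| Visit 16, 2-week follow-up | plus 15 | 13 |
| Visit 17, 4-week follow-up | plus 16 | 14 |

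**Within a period.** Between the baseline and week-3 questionnaires the participant receives the baseline, Day 4, week 1 and week 2 results. That is 4 sets in each period.

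**Sensitivity to the visit list.** The Participant follow up paragraph gives a shorter list of clinic visits that omits baseline and Day 4. Even on that list, the week 1 and week 2 results (2 sets) fall between the two questionnaires.

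**Length of the wait if results are withheld.** Each period is 3 weeks plus 4 weeks of follow-up, or 7 weeks. Two periods give 2 × 7 = 14 weeks from baseline to Visit 17, assuming that the second baseline follows directly on the first period's last follow-up.

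**Size of the bias.** The protocol gives no SD, no expected change in symptoms or LYMQOL, and nothing on how strongly participants respond to their results. No magnitude can be derived.

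**The case against.** The strongest objection is symmetry. Results are returned on the same schedule in both periods. If the pad does nothing to volume or fluid, the results will look alike on average in the two periods and give no systematic reason to rate the pad period better. Any difference in self-ratings would then come mainly from knowing the allocation, which withholding printouts does not change. This stands as a limit on size. A reader might be tempted to assume a shift in scores and an SD and turn the concern into a false-positive rate. The documents do not support that: both inputs would be invented, and the result would not isolate feedback from knowledge of allocation. Symmetry does not remove the concern, because equal handover does not mean equal reaction when the participant knows the condition.

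Second, the self-ratings are not in the hypothesis, aims or numbered measurement objectives, and Doppler results are not among the data returned. This is correct. The exposure is greatest for secondary, self-rated outcomes and is indirect for volume and fluid.

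Third, there is some monitoring. A diary is reviewed at the phone call, Day 4 and weeks 1–3 of each period. Medications are recorded at each clinic visit, and exercise and care routine are asked about at baseline. This helps, but the diary's content is not stated and its review stops before the follow-up visits.

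Fourth, participants value their results. They would still receive all of them, only later.

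A reader might also infer that the plan treats agreement between measured and perceived change as independent corroboration. The protocol makes no such claim, so that is no part of this point.

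**Conclusion.** The concern holds as an avoidable weakness in conduct. The plan returns interim outcome data to unmasked participants before every questionnaire: up to 5 sets before the first post-baseline scores, up to 14 before the last, and 4 within each baseline-to-week-3 interval. These counts rest on Table 1 and on taking the handover sentence literally.

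The document shows that self-ratings and self-care can respond. It does not show that they will, in which direction, or by how much. The bias is additional to the larger one from knowing the allocation. A reader should not conclude that this feature alone invalidates the volume, fluid or blood-flow results, since nothing in the protocol supports so strong a claim. It merits correction because it cannot be repaired in the analysis and is cheap to prevent.

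**What to change.** Amend the sentence on returning results so that individual perometer and BIS printouts are given as a full set after the participant's final visit (Visit 17 for those who complete both periods) or at withdrawal. State that any finding needing medical attention is still told to the participant at once. Make the same change in the information sheet.

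Completing LYMQOL and the symptom scale before that day's measurements is optional good practice. It does not correct a stated defect, because the copy is handed over only when the visit ends.

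Cost: participants wait about 14 weeks from baseline for a benefit now promised at each of 15 clinic visits, and the protocol and information sheet need an ethics amendment. No extra visits, equipment or participants are required.
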